12.8.2.2.3 Temporary Suspension of Randomization/Allocation and Vaccinations

Section 11.5 Study Stopping Guidance outlines the procedure for DSMB ad hoc review due to the events listed in Section 12.8.2.2 Ad hoc DSMB Reviews. If during the ad hoc review, the DSMB determines that a temporary halt in randomization/allocation is required, participants who received vaccination prior to the temporary halt will continue in the study as planned. During the halt in randomization/allocation, recruitment, screening and consenting may continue, but no additional study vaccine doses will be administered.

13. Statistical Considerations and Analytical Plan

13.1 Overview

This is a randomized, multi-site, adaptive, open-label clinical trial comparing the immune response of different additional doses of COVID-19 vaccine in participants with autoimmune disease requiring IS medications. All study participants will have negative serologic or suboptimal responses to an initial COVID-19 vaccine regimen (Adult and Pediatric Stage 1) or a negative, suboptimal, or low immune response to initial COVID-19 vaccine regimen plus additional COVID-19 vaccinations (Adult and Pediatric Stage 2). We will focus on 5 autoimmune diseases in adult participants (SLE, RA, MS, SSc, and pemphigus) and 4 autoimmune diseases in pediatric participants (JIA, pediatric SLE, JDM, and POMS).

The primary objective is to determine the proportions of adult and pediatric participants who have a protective antibody response at Week 4 assessed by the NIAID-VRC MSD 3 plex (Wu-1 full-length spike, RBD, and N proteins) assay.

Response will be assessed within subgroups defined by the magnitude of immune response to prior vaccines, age, categories of IS medications, type of vaccine, and whether IS medications are continued or withheld around administration of the additional homologous vaccine dose.

13.2 Endpoints

Primary, secondary, and exploratory endpoints are listed in Sections 3.2 Primary Endpoint, 3.3 Secondary Endpoints, and 3.4 Exploratory Endpoints, respectively.

13.3 Measures to Minimize Bias

Participants will be assigned to cohorts defined by IS medication (Cohort A and D: MMF/MPA; Cohort B and E: MTX; and Cohort C and F: BCDT) and by the initial COVID-19 vaccine regimen received (Moderna COVID-19 Vaccine, Pfizer-BioNTech COVID-19 Vaccine, or Janssen COVID-19 Vaccine). In Adult Stage 1 and the pediatric portion of the study, participants in Cohort C will be allocated to continue taking their prescribed IS medications throughout the trial. Participants in Cohort A and B will be randomized in a balanced fashion (1:1), within the cohorts defined by IS medication and initial COVID-19 vaccine regimen, to one of the available IS medication treatment plans (continue IS vs. withhold IS). Randomization will be performed using a permuted block design stratified by disease type.

13.4 Analysis Plan

13.4.1 Analysis Populations

The following populations will be defined separately for Stage 1 and Stage 2.

Vaccinated population: will be defined as all participants who are randomized or allocated and receive study vaccine in the study. For all endpoints, participants will be evaluated by the actual vaccine received. In Cohorts A and B, participants will be analyzed in subgroups defined by randomized assignment to continue or withhold IS medications in the primary analysis.

Per protocol populations: will be defined as the subgroup of participants in the vaccinated population who adhere to the treatment plan for IS medications defined in Section 7.1.1 Protocol-mandated Medications and have no major protocol deviations or ineligible entry criteria that would impact the vaccine response assessment at Week 4.

Safety population: will be defined as all participants who initiate the treatment plan for IS medications or receive an additional dose of vaccine.

13.4.2 Primary Analysis of Primary Endpoint

The primary endpoint of a protective antibody response will be the proportion of participants who reach the laboratory-defined threshold for the NIAID-VRC MSD 3 plex (Wu-1 full-length spike, RBD, and N proteins) assay. Participants with missing Week 4 anti-COVID-19 antibody response data with a documented COVID infection will be considered as not having a protective antibody response. All other participants missing Week 4 anti-COVID-19 antibody response data will be considered to be missing-completely-at-random (MCAR). Intercurrent events which result in Week 4 anti-COVID-19 antibody response data being unevaluable for immune response, including receipt of monoclonal antibodies or plasma products directed against SARS-CoV-2 and any SARS-CoV-2 vaccine outside of the study, will also result in data being considered to be missing-completely-at-random (MCAR).

The primary analysis will be evaluated independently within each arm (defined by age, cohort, vaccine, and IS treatment plan) and within subgroups with either a negative or suboptimal response to prior vaccines (defined as Roche Elecsys® Anti-SARS-CoV-2 S result \leq 200 U/mL) or with a low immune response (defined as Roche Elecsys® Anti-SARS-CoV-2 S result $>$ 200 U/mL and \leq 2500 U/mL). The primary analysis will be performed in the vaccinated population. The proportion of participants meeting a protective antibody response criteria will be reported in each arm and subgroup with 90% Clopper-Pearson confidence intervals and analyzed using a one-sided exact test with alpha = 0.05 against the null hypothesis that the probability of achieving a protective immune response is \leq 0.25. P-values will not be adjusted for

multiple comparisons. The primary analysis will also be conducted in the subgroup of participants with a Roche Elecsys® Anti-SARS-CoV-2 S result ≤ 50 U/mL at the Screening visit. Each analysis will occur after the evaluable participants assigned to that arm have completed the Week 4 study visit or are withdrawn from the study.

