Originally, participants who previously received 3 total doses of a single mRNA vaccine (Moderna COVID-19 Vaccine OR Pfizer-BioNTech COVID-19 Vaccine) received their choice of either the Janssen vector-based COVID-19 vaccine or the other mRNA COVID-19 vaccine.

Beginning with v4.0 of the protocol, this trial will not utilize the Janssen vector-based COVID-19 vaccine. Participants who previously received 3 total doses of a single mRNA vaccine will receive a choice of an alternative mRNA COVID-19 vaccine or the Sanofi-GSK protein-based COVID-19 vaccine. Participants who previously received 4 or more doses of a single mRNA vaccine or 3 or more doses of a mixture mRNA vaccines (Moderna COVID-19 Vaccine AND Pfizer-BioNTech COVID-19 Vaccine) will receive the Sanofi-GSK protein-based COVID-19 vaccine.

Participants who previously received 2 doses of the Janssen vector-based COVID-19 vaccine will receive the Moderna COVID-19 Vaccine. This alternative Moderna dose will be a full vaccine dose, not a reduced vaccine booster dose.

Beginning with v6.0 of the protocol, bivalent versions of the mRNA vaccines, Moderna and Pfizer-BioNTech COVID-19 vaccines, replaced original monovalent versions. In addition, autoimmune disease patients with a negative or suboptimal serologic response to the initial COVID-19 vaccine regimen (defined as an Elecsys® Anti-SARS-CoV-2 S result ≤ 200 U/mL at the Screening visit), or with a low immune response (defined as an Elecsys® Anti-SARS-CoV-2 S result > 200 U/ml and ≤ 2500 U/mL at the Screening visit) are eligible to receive an additional or homologous or alternative vaccine dose. The threshold of Roche Elecsys® anti-RBD assay ≤ 2500 U/ml SARS-CoV-2 S antibody concentration has been chosen based on a study of immunosuppressed organ transplant candidates, which showed that low anti-RBD titers after the third dose of mRNA-1273 was associated with low prevalence of Omicron BA.1 neutralizing antibodies [35]. In addition, a recent study using a cohort of health-care workers estimated that subsequent Omicron BA.4/5 neutralizing titers may be as much as 5-fold lower [36].

Cohort-defining IS medications (MMF/MPA and MTX) will be held by all participants around the time of vaccination, as appropriate, in an effort to improve the likelihood of a robust response to the alternative vaccine.

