2.2.2 Stage 2 Secondary Objectives

These secondary objectives are applicable to both the adult and pediatric populations.

- To determine the proportions of participants with a negative serologic or suboptimal response to a previous COVID-19 vaccine administration who develop a protective antibody response after receiving a subsequent alternative vaccine dose, evaluated using the NIAID-VRC MSD 3 plex (Wu-1 full-length spike, RBD, and N proteins) assay.

- To assess the immune response following a subsequent alternative vaccine dose in the subgroup of participants that had a low immune response following a previous COVID-19 vaccine dose.
- To determine the incidence of seroconversion following a subsequent alternative vaccine dose in the subgroup of participants that are anti-COVID-19 antibody negative following a previous COVID-19 vaccine dose.
- To determine the incidence of AEs, including MAAEs, NOCMCs, and SAEs following a subsequent alternative COVID-19 vaccine dose.
- To assess whether responses to a subsequent alternative COVID-19 vaccine dose differ by type of vaccine administered.
- To assess whether responses to a subsequent alternative COVID-19 vaccine dose differ by type of cohort-defining IS medications and by disease type.
- To assess whether response to a subsequent alternative COVID-19 vaccine dose is associated with corticosteroid dose at the time of vaccination.
- To assess whether response to a subsequent alternative COVID-19 vaccine dose is associated with clinical parameters including disease activity, co-morbid illness, age, and sex.
- To determine whether disease activity is increased following a subsequent alternative COVID-19 vaccine dose, and if so, whether immunologic variables are associated with increased disease activity and/or vaccination response.

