8.1.4.5 Mechanistic Specimens

- Serum
 - Antibody levels will be tested at each time point to test for IgG and immunoglobulin M (IgM) responses against SARS-CoV-2 spike, receptor binding domain, and nucleocapsid proteins.
- Whole blood/peripheral blood mononuclear cell (PBMC)/plasma/DNA
- RNA assays

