13.6 Statistical Hypotheses

The set of null hypotheses are that the true probability of a protective antibody response, π , is ≤ 0.25 in a given subpopulation, representing an inadequate improvement in anti-COVID-19 Antibody Response after administration of

an additional vaccine dose to warrant further investigation in that subpopulation. This will be tested within each arm indexed by cohort and age group (i), additional vaccine dose (j), and IS treatment plan (k)

$$H_{0,(i,j,k)}: \pi_{(i,j,k)} \leq 0.25$$

The set of alternative hypotheses are that the true vaccine response rate, π , is >0.25 and may warrant further investigation in that subpopulation

$$H_{1,(i,j,k)}: \pi_{(i,j,k)} > 0.25$$

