13.7 Sample Size Considerations

Early reports show that a significant number of individuals taking IS medications respond poorly or not at all to COVID-19 vaccination. Ruddy et al. reported 26% of chronic inflammatory rheumatic disease patients had undetectable SARS-CoV-2 antibody response after their first mRNA vaccine dose, but many seroconverted with the second dose such that only 6% had persistent undetectable SARS-CoV-2 RBD antibodies [16]. However, those taking MMF or rituximab were at much higher risk of not mounting a detectable antibody response (89% and 67%, respectively)[17]. Another report has demonstrated diminished overall serologic response in adults with chronic inflammatory diseases, particularly in those treated with B-cell depletion or antimetabolites including MTX, with a 50-fold and 3-fold reduction in post-vaccine antibody titers relative to immunocompetent controls[80].

Based on the emerging evidence in individuals taking IS medications, an ineffective rate of achieving a protective immune response after the additional vaccine dose was defined to be less than or equal to 0.25 (null hypothesis). The study is powered to reject the null hypothesis in each arm when the true response rate is 0.5 or greater as preliminary evidence the additional vaccine dose is effective in specific study population.

The proportion of participants in each arm (cohort, additional vaccine dose, and IS treatment plan group) to receive an additional vaccine dose and achieve a protective antibody response at Week 4 will be evaluated using a one-sided exact test with alpha = 0.05 to test against a null hypothesis that the true response rate is ≤ 0.25 . A sample size of 33 evaluable participants achieves at least 90% power to reject null hypothesis when the true response rate is 0.5 or greater.

Secondary analyses will compare the rate of achieving a protective immune response across arms using the multivariable logistic regression model. For comparisons of single arms, 33 evaluable participants per arm will provide 80% power to detect an odds ratio of 4.2 when the null hypothesis is true in one arm (improvement from 0.25 to 0.584). For comparisons that combine arms, pooling 3 arms (e.g., type of additional vaccine dose) will provide 80% power to detect an odds ratio of 2.3 (improvement to 0.394).

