8.2. Primary Endpoint

The primary endpoint of a protective antibody response will be the proportion of participants who reach the laboratory-defined threshold for the NIAID-VRC MSD 3 plex (Wu-1 full-length spike, RBD, and N proteins) assay at Week 4. The Wu-1 full-length spike protein will be used in determining a protective antibody response in the primary analysis; the RBD protein will be used in secondary analyses of antibody response; and N proteins will be used in supportive analyses as evidence of COVID infection.

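### The primary test is on a Week 4 level with no Week 0 condition, so in the >200 to 2500 U/mL stratum rejecting 0.25 does not by itself show that the dose improved the response

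*Protocol*

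**What the plan says.** Protocol 13.4.2 defines the endpoint: "The primary endpoint of a protective antibody response will be the proportion of participants who reach the laboratory-defined threshold" of the NIAID-VRC MSD assay. The assessment is at Week 4 (Protocol 3.2). The proportion is analysed with a "one-sided exact test with alpha = 0.05 against the null hypothesis that the probability of achieving a protective immune response is" at most 0.25. This is done in each arm and separately in the ≤200 U/mL and the >200 to 2500 U/mL Elecsys strata, without multiplicity adjustment. Protocol 13.4.4 repeats the analysis for Stage 2.

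Protocol 13.6 describes a true rate at or below 0.25 as "representing an inadequate improvement in anti-COVID-19 Antibody Response". Protocol 13.7 says that "an ineffective rate of achieving a protective immune response after the additional vaccine dose was defined to be less than or equal to 0.25", and treats rejection as preliminary evidence that the dose is effective.

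SAP 8.2 names the deciding antigen: "The Wu-1 full-length spike protein will be used in determining a protective antibody response in the primary analysis". That SAP follows protocol version 3.0 and plans primary analyses only at ≤200 and ≤50 U/mL. The higher stratum exists only in the current protocol.

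Week 0 values are used elsewhere: seroconversion in Week 0 negatives, descriptive fold rise in Week 0 positives, longitudinal summaries, and a negative/positive covariate in the supportive model (Protocol 13.4.3 and 13.4.4; SAP 8.2.4 and 8.3).

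**The concern.** The tested quantity is a level at one visit. The interpretation attached to it is a change caused by the dose. The two agree only when few participants start above the threshold.

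That is a reasonable expectation for people with little or no antibody, and those are the people whose data justify 0.25 in Protocol 13.7. It is less secure in the >200 to 2500 U/mL stratum. The same 0.25 already appears in the SAP, when entry stopped at 200 U/mL, and it was carried over unchanged. Protocol 1.2.1 reports average primary-series responses of 2,079 to 4,435 U/mL in healthy populations, so the 2500 ceiling overlaps ordinary responses. Entry is limited on the Elecsys scale, so eligibility does not guarantee a Week 0 MSD value below the threshold.

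Every arm receives a dose, and each is tested alone against a fixed rate. If enough participants start above the threshold, an arm could be reported as showing an effective dose when titres had not moved.

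**Working it through.** **Inputs.** Null rate 0.25, alternative 0.50, one-sided exact test at 0.05, 33 evaluable (Protocol 13.4.2 and 13.7); 40 enrolled per stratum (13.7). The share q already above the protective threshold at Week 0 is in neither document, so it is an assumption shown over a range.

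**The plan's own figure.** The critical value r is the smallest with P(X ≥ r | n, 0.25) ≤ 0.05. For n = 33, r = 13 (39.4%), and the actual size is 0.0484. Power is P(X ≥ 13 | 33, 0.50) = 0.919. With n = 32, r is again 13 and power is 0.892. So 33 for at least 90% power is reproduced.

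**No vaccine effect.** If a fraction c of those below the threshold cross it, and those above stay above, the Week 4 rate is q + (1 − q)c. With no effect and stable titres c = 0, so the rate equals q and the chance of rejection is P(X ≥ r | n, q). For n = 40, r = 16 and the size is 0.026.

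| Assumed q | n = 33, r = 13 | n = 40, r = 16 |
|---|---|---|
| 0.20 | 0.008 | 0.003 |
| 0.25 | 0.048 | 0.026 |
| 0.30 | 0.161 | 0.115 |
| 0.40 | 0.594 | 0.560 |
| 0.50 | 0.919 | 0.923 |
| 0.60 | 0.995 | 0.997 |

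The chance passes 5% once q exceeds about 0.25 (n = 33) or 0.27 (n = 40). For n = 33 it reaches 50% at q of about 0.38 and 90% at about 0.49.

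**What the design alternative then means.** If q = 0.40, a Week 4 rate of 0.50 needs only c = (0.50 − 0.40)/(1 − 0.40) = 0.167. Only one in six of those below the threshold would have to cross it.

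**Restricting to those below the threshold at Week 0.** With no effect and stable titres, the expected crossing rate is about 0 whatever q is. Starting from 33 evaluable, the number left is about 33(1 − q):

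| Assumed q | Testable | r | Size | Power at 0.50 | Evaluable needed to keep 33 testable, 33/(1 − q) |
|---|---|---|---|---|---|
| 0.25 | 25 | 11 | 0.030 | 0.788 | 44 |
| 0.40 | 20 | 9 | 0.041 | 0.748 | 55 |
| 0.50 | 16 | 8 | 0.027 | 0.598 | 66 |

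**Whether planned analyses already close the gap.** Seroconversion uses the MSD spike positivity cut-off (1,204.71 AU/mL, SAP 8.3.1), which is not stated to be the protective threshold. Fold rise is descriptive. In the supportive model, if baseline status is taken on the Elecsys cut-off (0.79 or 0.80 U/mL), everyone above 200 U/mL is positive and the term cannot adjust within this stratum. None of these changes the primary decision.

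**The case against.** The endpoint matches the primary objective. Protocol 2.1 asks what proportion have a protective response at four weeks, and the Week 4 proportion answers that. A reader might infer that the objective requires a newly acquired response, because Protocol 2.2.2 speaks of participants "who develop a protective antibody response after receiving a subsequent alternative vaccine dose". That is a Stage 2 secondary objective confined to negative or suboptimal responders, and it does not cover the higher stratum. This part of the objection stands, and it is why the primary endpoint should not be replaced.

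The size has no anchor. No protective threshold is stated, and SAP section 12 allows that none may be available at a preliminary analysis, in which case the primary test is not run then. The documents do not favour a Week 0 share of 30% to 60% over one below 25%, where the nominal level holds. This also stands.

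A reader might infer that the antigen makes matters worse: the 2500 ceiling rests on a finding that "low anti-RBD titers after the third dose of mRNA-1273 was associated with low prevalence of Omicron BA.1 neutralizing antibodies", while success is judged on ancestral spike. Neither document says that these participants are less deficient against ancestral spike. Nor does either pair this stratum with that antigen, since the antigen is named only in a SAP that predates the stratum. Carry-over from an earlier study dose is also a weak addition. Rollovers must have an Elecsys result within 4 weeks of Stage 2 baseline, so residual antibody is already reflected in their stratum.

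Finally, this is a phase II trial whose conclusions are worded as preliminary, and a stratum with no rise would show a fold change near 1. That limits the harm. It does not repair the stated reading of the primary test.

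**Conclusion.** The mismatch is in the text and should be fixed: a Week 4 level is tested, and rejection is read as adequate improvement and evidence of an effective dose. In the >200 to 2500 U/mL stratum, 5% protection against that reading holds only if about 25% or fewer are above the threshold at Week 0 (about 27% with 40 evaluable). Beyond that, with 33 evaluable and stable titres, the chance of rejecting with no vaccine effect is 16%, 59%, 92% or 99.5% at assumed shares of 30%, 40%, 50% or 60%. Waning between Week 0 and Week 4 would lower these figures.

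The documents do not support saying that this error rate will occur, because the threshold and the Week 0 share are both unknown. They also do not support calling the Week 4 proportion an invalid endpoint. The ≤200 U/mL stratum has the same gap in principle, but a high Week 0 share is less likely there.

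**What to change.** Keep the Week 4 proportion as the primary endpoint, in line with Protocol 2.1. In Protocol 13.4.2 and 13.4.3, and in the updated SAP 8.2:

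- (a) Report, for each arm and Elecsys stratum, the share above the same MSD threshold at Week 0.
- (b) Add a prespecified key supportive analysis: the proportion at or above the threshold at Week 4 among those below it at Week 0, with the exact interval and the exact test against 0.25. Summarise those already above by fold rise.
- (c) State in 13.6 and 13.7 that rejection alone shows a Week 4 level above 25%. A claim of improvement or effectiveness in the >200 to 2500 U/mL stratum then requires support from (b).

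No new sampling is needed. Protocol 8.1.4.5 already provides that "Antibody levels will be tested at each time point to test for IgG and immunoglobulin M (IgM) responses against SARS-CoV-2 spike", and Week 0 serum is in the schedules of events. SAP section 2 already expects updates.

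The cost is precision. With 40 per stratum as the cap, (b) may have 20 testable and power 0.75 if 40% start above the threshold, or 16 and 0.60 if half do, so in some arms it may be descriptive only. Using 0.25 as the null in this restricted group also needs a sentence of justification. Redefining the primary endpoint in both strata and both stages would impose that loss of power on the main test. It would also change the endpoint for Adult Stage 1, which closed on 15 August 2022 and never included this stratum.

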13.4.3 Supportive Analyses of the Primary Endpoint

Supportive analyses will also use a multivariable regression model on the entire vaccinated population in order to estimate the rates of vaccine response within and across arms (age group, cohort, vaccine, and IS treatment plan group) using the logistic link function, and including baseline covariates for disease type (SLE, RA, MS, SSc, and pemphigus in adults and JIA, pediatric SLE, JDM, and POMS in pediatrics) and immune response to the initial COVID-19 vaccine regimen (anti-COVID-19 antibody negative or positive). Descriptive statistics will be used to summarize antibody response to the additional homologous vaccine dose on a continuous scale. Estimates of the average antibody response and variance within and across cohorts will be obtained from a multivariate general linear regression model. Based on published data on the assays, it is anticipated that log-transformation of assay values will allow for Gaussian assumptions to hold, but alternative Box-Cox transformations of the data may be explored to stabilize the variance.

The primary and supportive analyses will also be replicated on the Per-protocol population and using alternative strategies for missing data.

